## **Study Design**

This study will be designed as a prospective clinical trial to compare various energy-based devices for the improvement of the scalp, face, neck/décolletage, trunk, hands, upper and lower extremities, and vagina. If patients meet the inclusion and exclusion criteria for multiple treatment areas, they will be allowed to receive treatment for multiple areas. The treating physician will decide which energy-based device is best-suited to address the patients' aging concerns; although patient preference will be taken into account, ultimately the treating physician is responsible for the correct assessment of the patients' needs, the use of the appropriate energy-based devices, and the final treatment. Although this may lead to some bias, patients will be treated in the most appropriate manner for their disease. Patients will be followed for 3 months post-treatment to determine if the procedure was efficacious for rejuvenation of the treatment anatomical area.

Per statistical considerations outlined below we will be comparing non-ablative and ablative devices. For each body area studied, 10 patients will be enrolled each into the non-ablative and the ablative device groups. The decision to treat and which device will be used will be made by the physician after careful consideration of a subject's rejuvenation concern(s). Multiple devices may be used due on one subject; for instance, a subject may require facial, body and/or vaginal rejuvenation, in which case one of the devices such as the Fraxel, Halo, Helios, Vbeam, or PicoWay would be used to address the face or body with the device picked based on the subject's needs or concerns, while either the ThermiVa or the DiVa would be used for vaginal rejuvenation, and PALLAS would be used for the scalp or hypopigmentation concerns.

A retrospective electronic medical record review will also be completed as part of this study to capture patients who were previously treated with any of the aforementioned modalities for rejuvenation of either the face, neck/décolletage, hands, trunk, upper and lower extremities and/or vagina.

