The study endpoint will be 3 months. Number of laser treatments needed during this time period will be based on the patient's clinical response to each treatment (as assessed by the physician). Evaluation will occur using various validated methods including photographs, MPM imaging, the Global Aesthetic Improvement Scale, the Visual Analogue Scale, the Modified Fitzpatrick Wrinkle Scale, the Wrinkle Severity Rating Scale, the Facial Laxity Improvement Scale, the Dyspigmentation Scale, the Mid-Clavicular Nipple Distance, the Fabi Bolton Chest Wrinkle Scale, the Merz Hand Grading Scale, the Vulvo-vaginal Laxity Questionnaire, Female Sexual Function Index, International Consultation on Incontinence Questionnaire – Short Form, Severity of Alopecia Tool, Psoriasis Scalp Severity Index, Patient Global Impression of Change, and Clinician Global Impression (based on which body site and laser are used).

There are no composite variables as the primary outcomes will only be determined by the physician and subject GAISSs. Other criteria for evaluation (secondary and exploratory outcomes) include photographs, the Modified Fitzpatrick Wrinkle Scale, the Wrinkle Severity Rating Scale, the Facial Laxity Improvement Scale, the dyspigmentation scale, the mid-clavicular nipple distance, the Fabi Bolton Chest Wrinkle Scale, the Merz Hand

Grading Scale, the Visual Analogue Scale for pain, the patient diary, and the investigator-authored patient satisfaction survey.

At each study visit, the investigator/physician will collect physician and subject-reported data regarding the efficacy and adverse events associated with the procedure (Visits 2-5, Days 14-90). To define patient satisfaction, an investigator-authored survey will be completed at the last visit (Visit 5, Day 90). Photographs will be collected at all visits (Visits 1-5, Days 1-90).

Since use of the PALLAS laser is typically required twice weekly, treatment of scalp and hypopigmentation disorders will follow a separate schedule of events from the other energy-based devices. Subject will receive 24 treatments over 12 weeks (Visits 1-24), with patient and clinician assessments and clinical photos taken at every other visit (Visit 2, 4, 6, 8, 10, 12, 14, 16, 18, 20, 22, 24). A blinded clinician will also assess change in skin or hair at Visit 12 and 24. Visit 25 will consist of a one-month follow up after the three-month treatment period.

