## **STATISTICAL ANALYSIS PLAN**

Statistical analysis of the data will be limited given the small sample size. Given the scales used for evaluation, data will be recorded as continuous scores. Statistical analysis will be completed using non-parametric methods (with significant defined as  $p < 0.05$ ) due to the subjective nature of the quantitative scales of improvement used and possible skew of results. Given that multiple areas will be treated and monitored for improvement over time, we may need to apply the Bonferroni Correction. If and when dependent samples are reported (i.e. longitudinal measures on individual patients), analysis will be completed with either the Mann-Whitney-Wilcoxon Test (two observations) or Friedman's test (more than two observations). When possible, trend evaluated over time will be assessed using a non-parametric test for trends over ordered groups. Bonferroni correction will be used to account for multiple comparisons. Analysis will be completed using STATA, version 13.

Power and sample size will be determined based on primary outcome- to compare the improvement between ablative and non-ablative therapy in face, décolletage, hands, trunk, upper and lower extremities, and vagina. Given the 7 regions to compare, Bonferroni correction was used to define the new significance level as  $0.05/7=0.007$ . Sample sizes of 10 in ablative and 10 in non-ablative group in each body region achieve 81% power to show a difference in means when there is a difference of 2.0 between the null hypothesis mean difference and the actual mean at the 0.007 significance level (alpha) using a two-sided Mann-Whitney-Wilcoxon Test.

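### The trend over time is to be tested across ordered groups that are visits of the same patients, so its error rate is wrong, in a direction that depends on the correlation pattern and the visit schedule

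*Combined protocol and SAP*

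**What the plan says.** The Statistical Analysis Plan has two sentences on repeated measurements. One describes "longitudinal measures on individual patients" as dependent samples and assigns a Wilcoxon-type test to two observations and Friedman's test to more than two. The next states, with the qualifier that this applies when possible, that "trend evaluated over time will be assessed using a non-parametric test for trends over ordered groups". It names no specific test and does not mention blocking by patient.

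The data come from the Study Design section. On the standard laser schedule, outcome data are collected after treatment at "Visits 2-5, Days 14-90", which is four assessments per patient. On the PALLAS schedule, assessments are made at every even visit from 2 to 24, which is twelve during treatment, plus a follow-up at Visit 25. On numbers: "For each body area studied, 10 patients will be enrolled each into the non-ablative and the ablative device groups".

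**The concern.** Because the trend is over time, the groups being ordered are the visits, and the same patients fill every group. Rank tests for trend across ordered groups, such as Cuzick's or the Jonckheere-Terpstra test, derive their variance from independent groups. Applied to visits, they leave stable differences between patients in the error term and ignore any link between neighbouring visits.

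At stake is whether improvement builds or fades up to the 3-month endpoint. A wrong variance can hide a real trend or produce a false one, and the plan as written does not tell the reader which to expect.

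**Working it through.** **Figures in the plan.** None is given for the trend test. The adjusted level reproduces (0.05/7 = 0.0071, stated as 0.007). The 81% power is for the between-group comparison, has no SD behind it, and does not bear on this point.

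**Inputs.** From the documents: 10 patients per group and body area; 4 post-treatment assessments (standard schedule) or 12 on-treatment assessments (PALLAS). Assumed, because the documents are silent: within-patient correlation ρ of 0.3, 0.5 or 0.7, either equal between all visits or decaying by visit (AR(1)); evenly spaced visits; 10 patients on the PALLAS schedule too; a linear rise of 0.75 SD from first to last visit for power; two-sided nominal 5%.

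**Analytic check, 4 visits.** Take the linear contrast c = (−3, −1, 1, 3), with c′c = 20. Independent groups imply a variance proportional to 20.

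- Equal correlation: true/assumed variance = 1 − ρ = 0.70, 0.50, 0.30. The z statistic shrinks by √(1 − ρ), so a correct z of 1.96 becomes 1.64, 1.39, 1.07. A correct p of 0.05 is reported as about 0.10, 0.17, 0.28.
- AR(1): true/assumed variance = 1 + 0.5ρ − 0.6ρ² − 0.9ρ³.
  - ρ = 0.3: 1 + 0.15 − 0.054 − 0.0243 = 1.07
  - ρ = 0.5: 1 + 0.25 − 0.15 − 0.1125 = 0.99
  - ρ = 0.7: 1 + 0.35 − 0.294 − 0.3087 = 0.75

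The direction therefore already turns on the correlation pattern: clearly conservative in the first case, close to correct at low and moderate ρ in the second.

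**Simulated false-positive rate of the ordered-groups test (Cuzick type), nominal 5%.** 20,000 runs at 4 visits, 5,000 at 12.

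| Setting | ρ = 0.3 | ρ = 0.5 | ρ = 0.7 |
|---|---|---|---|
| 4 visits, equal correlation | 2.1% | 1.1% | 0.2% |
| 4 visits, AR(1) | 5.6% | 5.4% | 3.3% |
| 12 visits, equal correlation | 2.4% | 1.1% | 0.3% |
| 12 visits, AR(1) | 11.3% | 16.9% | 21.8% |

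Smaller separate runs agree within simulation error; at 4 visits under AR(1) they gave 5.1–6.8%, 4.8–5.6% and 2.6–3.4%. With scores rounded to 5 levels, the first row becomes 2.5%, 1.1%, 0.4%.

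**Comparison with within-patient tests, 4 visits, equal correlation, rise of 0.75 SD (3,000 runs).**

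| Test | False positives (ρ = 0.3 / 0.5 / 0.7) | Power (ρ = 0.3 / 0.5 / 0.7) |
|---|---|---|
| Ordered groups | 2.7% / 1.0% / 0.2% | 38% / 37% / 37% |
| Per-patient slope, signed-rank | 5.3% / 4.7% / 5.3% | 45% / 59% / 80% |
| Page's test | 5.9% / 5.4% / 5.3% | 46% / 60% / 79% |

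**The same tests when correlation decays.** The slope test gave 4.4–4.7% false positives at 4 visits under AR(1) and stayed at about 5% in the other settings. This is expected: each patient contributes one slope and slopes are independent between patients, so the level does not rest on the correlation between visits. Its power at ρ of 0.3–0.5 over 4 visits was 33–36%, against 39–42% for the ordered-groups test. Page's test was liberal: about 8–10% at 4 visits and 11–25% at 12.

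**The case against.** The strongest reply is that the plan names no test, qualifies the analysis as done when possible, and has just recognised longitudinal measures as dependent. An analyst might therefore choose a blocked version. What stands is that neither Cuzick's nor the Jonckheere-Terpstra test is written in the plan; they are examples of what the wording describes. But the wording does describe a test across groups, and nothing directs the analyst to a within-patient form.

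Friedman's test is also planned for the same visits. It respects the pairing and can detect change: in the equal-correlation setting its power was 27%, 37% and 58% at ρ of 0.3, 0.5 and 0.7. A missed trend would thus not always pass unnoticed. Friedman's test does not use the order of the visits, however, so it does not replace a trend test.

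A reader might go further and infer that the p-values are always too large and real trends will be missed. The documents do not support this. They give no correlation structure; with decaying correlation the 4-visit test is near nominal at ρ of 0.3–0.5, and on the PALLAS schedule the error is reversed, towards false trends. With no correlation there is no error.

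Two limits also stand. The figures are at an uncorrected 5%, although the plan mentions Bonferroni correction. The separate micro-coring schedule was not examined.

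**Conclusion.** The point holds as a wrong error term, not as a general loss of power. A test that treats visits of the same patients as independent groups does not hold its nominal level, and the direction cannot be settled from the documents. For an assumed ρ of 0.3–0.7:

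- 4 visits, equal correlation: conservative, with fewer than half of the trends found at ρ = 0.7 that a within-patient test finds (37% against 80%).
- 4 visits, decaying correlation: little harm at 0.3–0.5, conservative at 0.7.
- 12 PALLAS assessments, decaying correlation: false positives at roughly two to four times the nominal rate.

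It would also be wrong to infer that the main result is at risk. The trend analysis is not the primary comparison, and the between-group test of ablative against non-ablative devices does not depend on it. The sentence should be changed, but it is not a reason to question the design.

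**What to change.** Replace the trend sentence in the Statistical Analysis Plan with: *For each patient, the slope of score on visit day will be computed, and the slopes will be tested against zero with the Wilcoxon signed-rank test.*

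The cost is one sentence and no new data. Patients who miss a visit can be kept as long as a slope can be computed from their remaining visits. The downside is small: where correlation decays quickly, power at 4 visits is somewhat below the apparent power of the ordered-groups test (the 33–36% against 39–42% above).

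Page's test should not be the lead remedy. It matches the slope test under equal correlation but does not hold its level when correlation decays with time.

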## STUDY PROTOCOL

### Background & Purpose of the Research

#### Primary Outcome:

1. To compare the efficacy of different non-ablative and ablative energy-based therapies for improvement in skin and skin appendages of the scalp, face, neck/décolletage, hands, upper and lower extremities, trunk and vagina.

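### The seven regional primary tests use single-step Bonferroni at 0.05/7; Holm's step-down keeps the same 5% family-wise error and never rejects less, and the adjacent p < 0.05 wording should be scoped in the same edit

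*Combined protocol and SAP*

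**What the plan says.** All the relevant text is in the Statistical Analysis Plan section of the combined protocol and SAP.

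- **Primary tests.** The comparison is ablative against non-ablative in "face, décolletage, hands, trunk, upper and lower extremities, and vagina", which makes seven regions when upper and lower extremities are counted separately. The level is set by "Given the 7 regions to compare, Bonferroni correction was used to define the new significance level as" 0.05/7 = 0.007.
- **Power.** Ten patients per group in each region are said to give 81% power for a difference of 2.0 "at the 0.007 significance level (alpha) using a two-sided Mann-Whitney-Wilcoxon Test". No SD is given.
- **General threshold.** Earlier in the section the non-parametric methods are introduced "with significant defined as" p < 0.05, with no limit on which tests this covers.
- **Correction, optional.** Because several areas are followed over time, "we may need to apply the Bonferroni Correction".
- **Correction, firm.** A few sentences later: "Bonferroni correction will be used to account for multiple comparisons".

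No step-down procedure and no simultaneous confidence intervals are planned.

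Two other places bear on which tests form the family. The Primary Outcome section covers "improvement in skin and skin appendages of the scalp, face, neck/décolletage, hands, upper and lower extremities, trunk and vagina", which adds the scalp. Study Design rests the primary outcomes on both the physician and the subject Global Aesthetic Improvement Scale (GAIS) ratings. Research Procedures and Study Design both let one patient be treated in several areas, so the regional tests may be correlated.

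**The concern.** Single-step Bonferroni holds every region to 0.05/7 whatever the other regions show. Holm relaxes the level after each rejection (0.05/7, then 0.05/6, and so on to 0.05) and still keeps family-wise error at 5%. In a trial whose SAP describes its own analysis as limited by small numbers, the fixed level may miss regional differences that a procedure with the same error guarantee would detect.

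The second issue is the decision rule. A reader who takes the general p < 0.05 sentence and the optional-correction sentence at face value could treat a regional p-value between 0.007 and 0.05 as significant. What would be at stake is the 5% family-wise error that the power statement is built on.

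**Working it through.** **Inputs from the documents.** Seven regional tests; per-test level 0.007, two-sided Mann-Whitney-Wilcoxon; 10 v 10 per region; difference 2.0; power 81%.

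**Assumed, because the documents do not say.** The SD; normal scores without ties; between-region correlation 0 or 0.5.

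**1. The plan's own figures.** 0.05/7 = 0.00714, so 0.007 is correct rounding, and 7 × 0.007 = 0.049. The rounding does no harm: with 10 v 10 and no ties, attainable exact p-values step from 0.00684 to 0.00893, so 0.007 and 0.00714 reject the same results. The 81% cannot be reproduced without an SD. It is matched by SD 1.09 (Mann-Whitney, normal data), 1.12 (t-test), 1.19 (logistic data) or 1.25 (normal approximation). Exact Mann-Whitney power at 0.007 is 88% at SD 1.0, 80% at 1.1, 71% at 1.2, 46% at 1.5 and 23% at 2.0.

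**2. Holm's rule.** Order the seven p-values. Compare the smallest with 0.05/7 = 0.00714, then the next with 0.05/6 = 0.00833, 0.05/5 = 0.0100, 0.05/4 = 0.0125, 0.05/3 = 0.0167, 0.05/2 = 0.025 and 0.05, stopping at the first failure. Every level is at least 0.05/7, so each Bonferroni rejection is also a Holm rejection. The 5% bound needs no independence assumption.

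**3. Size of the gain.** Simulation of seven exact Mann-Whitney tests, 40,000 runs per setting, SD 1.09, independent regions:

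| Regions truly different | Average power, Bonferroni | Average power, Holm | All of them found, Bonferroni → Holm |
|---|---|---|---|
| 1 | 81.2% | 81.2% | 81.2% → 81.2% |
| 2 | 81.1% | 81.2% | 65.9% → 66.0% |
| 3 | 81.0% | 83.1% | 52.9% → 59.1% |
| 4 | 81.0% | 85.3% | 43.0% → 56.1% |
| 5 | 81.1% | 87.5% | 35.0% → 55.2% |
| 6 | 81.0% | 90.3% | 28.5% → 60.9% |
| 7 | 81.0% | 93.8% | 22.8% → 71.8% |

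The Bonferroni figure for all seven agrees with 0.81^7 = 0.229. Almost nothing is gained with two true differences because the second Holm level, 0.00833, falls in the gap between attainable p-values 0.00684 and 0.00893.

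**4. Sensitivity, seven true differences.**

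| SD | Correlation | Bonferroni | Holm |
|---|---|---|---|
| 1.09 | 0.5 | 81.0% | 91.1% |
| 1.2 | 0 | 71.0% | 86.2% |
| 1.2 | 0.5 | 71.3% | 83.1% |
| 2.0 | 0 | 23.1% | 25.4% |
| 2.0 | 0.5 | 23.3% | 28.2% |

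A separate simulation gave 26% under Holm at SD 2.0 with independent regions.

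**5. Family-wise error.** With no true difference, independent regions and SD 1.09, both procedures simulate at 4.8%, and Holm did not exceed that for any number of true differences. Within the bound Holm's actual error can be higher than Bonferroni's: with six true differences, 0.7% becomes 3.4%.

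**6. If p < 0.05 were used for all seven.** 1 − 0.95^7 = 1 − 0.698 = 0.302 for independent tests at exactly 0.05; about 26.7% with the discrete exact test; about 21% at correlation 0.5. None of these needs an SD.

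**7. The family.** Including the scalp makes the first step 0.05/8 = 0.00625. Testing both GAIS ratings in seven regions makes 14 tests and a first step of 0.05/14 = 0.0036. Running a seven-test procedure separately for each rating would allow a family-wise error of about 1 − (1 − 0.05/7)^14 = 9.5% if independent, with a bound of 10%.

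**The case against.** Four objections deserve weight.

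- **Bonferroni is not an error.** This stands. The level is prespecified, correctly computed and matched to the power statement. A reader might infer that the regional analysis is invalid; nothing in the documents supports that.
- **Holm does not always find more.** This also stands. The chance of at least one true finding is essentially unchanged, and the gain is nil with one true difference and about 0.1 point with two. The large figures require all seven regions to differ by 2.0, which the documents nowhere predict, and an SD near 1.09, which they do not state. Tied GAIS scores would alter the power figures, though not the ordering of the two procedures.
- **The SAP does commit to a correction.** A reader might infer that it leaves regional results between 0.007 and 0.05 open to either call, with a 30% error rate. That goes too far. The firm sentence ("Bonferroni correction will be used to account for multiple comparisons") and the description of 0.007 as the new significance level make Bonferroni the natural reading for these tests. What remains is a wording conflict, because the p < 0.05 sentence carries no scope and the optional sentence was left in.
- **Holm brings a cost in intervals.** Matching simultaneous confidence intervals are less simple than under Bonferroni. None are planned, so this carries little weight here.

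**Conclusion.** The point holds as an efficiency gain with a secondary wording repair. Holm dominates single-step Bonferroni for these tests: same 5% bound, any dependence, no Bonferroni rejection lost. Conditional on SD 1.09, normal untied scores and independent regions, the gain in average power runs from nothing with one true difference to about 13 points with seven (81.0% to 93.8%). It is about 10 points with seven at correlation 0.5, and only about 2 to 5 points at SD 2.0 (the upper end at correlation 0.5). The 21–30% family-wise error describes what would follow if p < 0.05 were applied to all seven tests. It does not describe the plan on its natural reading.

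A reader might also take 81% as a guaranteed floor on power under Holm. The documents do not support that: the SD is missing, and Study Design enrols exactly the 10 per group used in the power statement, with no allowance for losses.

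**What to change.** 1. Replace the optional-correction sentence ("we may need to apply the Bonferroni Correction"), and the firm sentence ("Bonferroni correction will be used to account for multiple comparisons") so far as it applies to the primary tests, with: *The primary regional comparisons are tested two-sided by Holm's step-down procedure at family-wise 0.05; p < 0.05 is not the criterion for these tests.* Changing only one of the two would leave a contradiction behind.
2. In the same edit, define the family: physician GAIS, subject GAIS or both, and whether the scalp is included. Run Holm over every test in that family.
3. Keep 10 v 10. Keep 0.05/7 in the power calculation only if the family is seven tests, and label it the first Holm step rather than the fixed level for every region.
4. Describe 81% as per-region power at that first step under the assumed difference and SD, state that SD, and do not call the figure a minimum.

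The cost is SAP wording, plus a recalculated power statement if the family is not seven. No patients, visits or measurements change. The only statistical downside is less simple simultaneous intervals, should the sponsor later want them.
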